## Study Protocol:

**A) RECRUITMENT :** The principal investigator (PI) will use the following recruitment strategies: in-person recruitment and clinician referral through use of the study flyer/referral form.

**In-person recruitment:** The PI will be present at the health center(s) on multiple days/week when health care providers (HCPs) and clinic staff see patients. The PI will work closely with HCPs and clinic staff to identify eligible patients and to how/when best approach eligible patients to introduce them to the study, anticipating it might be at the end of the visit in the exam room. The HCPs and clinic staff will introduce the PI to potentially eligible patients to introduce the study prior to the PI approaching the patient. Once the patient expresses interest in learning more about the study or indicates they would like to participate, the PI will follow the procedures as outlined in the study procedure section below.

**Eligibility:** 1) adults aged 18 years and older 2) speak and understand English 3) personally own and use an Android or iOS smartphone which is capable of downloading the Medisafe app and 4) take at least 1 medication for a chronic illness based on their computerized medical record at the health center.

**Clinician referral:** Study flyer/referral forms will be available in the patient exam rooms and/or in the medicine department's clinician office as determined/approved by clinic staff. Once a clinician identifies a potentially eligible patient, they or the patient may complete the study flyer/referral form. If the PI is present at the clinic, the form can be given directly to the PI. If the PI is not available, they will place it in a locked and secured collection box labeled "Smartphone App Study" only accessible by the PI. The box will be located in the general medicine department's clinician office or the appropriate exam rooms or as otherwise deemed necessary by clinic staff. The box will be checked, and forms collected at least once a week by the PI. Any patients who fill out a form will be contacted via their preferred method i.e., phone call, email or text message (see scripts for a phone call, email or text message) within one week by the PI.

**Study flyer/referral form:** Study flyers/referral forms will provide study information and a place for patients interested in participation to provide their contact information as well as a space for the referring HCP signature to confirm that the patient's medications listed in the Electronic Medical Record are correct and up-to-date. The flyers will be kept in exam rooms deemed appropriate by clinic staff and will be returned to the HCP. The HCP will then either give them to the PI or place them in a secured collection box labeled "Smartphone App Study" which will only be accessible to the PI. The box will be checked at least once a week, and forms will be collected at that time by the PI.

## **B) STUDY PROCEDURES:**

Once patients are contacted, the completed flyer/referral forms will be placed in a locked file cabinet at the clinic accessible to only the PI. The patient's name, contact information and preferred mode of contact will be housed in REDCap, a HIPAA compliant, password protected database application.

**For patients who are available in-person:** If a patient expresses interest in participating, the PI will meet with the patient in a private room at the clinic to confirm eligibility, describe the study, answer questions and, based on patient preference, obtain e-consent using an iPad or a hard copy of the consent form. Once the patient is consented, the PI will obtain a printed-out copy of the patient's updated, current medication list from the EMR. The medication list will be reviewed by the PI to confirm that the patient regularly takes at least 1 prescribed medication for a chronic illness. Based on patient preference, the PI will then either give them a hard copy of the survey, or direct them to the REDCap survey on the PI's iPad. While patients complete the survey, the PI will remain in the room to be available should questions arise, but will be distanced away from the patient.

**For patients whose completed flyer/referral form is collected from the lock box:**

Once the PI contacts patients and they indicated an interest to participate, the PI will obtain their permission to email them the link to the IRB approved econsent form, which will be followed by the REDCap survey, if they prefer this method. If they prefer scheduling a time to complete this at the clinic, a time will be arranged.

**Informed consent:** For eligible patients interested in participation, the PI will obtain either in-person written consent or in-person IRB-approved e-consent via REDCap on an iPad. If the patient is not present in the clinic and would like to receive the IRB approved e-consent form via email, the patient will be sent an email link to the REDCap e-consent survey to access study information. Hard copies of consent forms will be kept in the locked file cabinet.

**C) DATA COLLECTION METHODS:**

**1.) Survey**

a)Baseline Data Collection (Time 1): Survey (both intervention and waitlist control groups): Once consent is obtained, the PI will administer the baseline questionnaire as either a hard copy survey or the REDCap electronic survey on a password protected iPad if the patient prefers. The patient will complete the baseline questionnaire independently, unless they ask for the PI to assist, in which case the PI will read each question to the patient with the patient indicating their answer on either the iPad or the hard copy survey. Only if the patient requests that the PI indicate their responses on the survey will the PI fill out the questionnaire for the patient. The PI will be present to answer any questions patients may have during data collection.

Hard copy surveys: The completed hard copy surveys will be kept in a locked file cabinet at the health center. All hard copy surveys will be assigned the unique study identifier (REDCap ID) and any patient identifiers will be removed / blacked out prior to storage. The PI will enter data collected using hard copy surveys once into the main REDCap database and into a second REDCap database to enhance data integrity by allowing for a comparison of the data entered, to identify inconsistencies between the two databases and to verify the correct data points by reviewing the hard copy surveys. This will be done prior to data analysis commencing.

*REDCap surveys:* As described earlier, patients might access the survey and complete consent and the study measures by using the REDCap survey link. If patients have not responded to the initial patient contact and completed the consent and survey within 2 weeks, two reminders will be sent by phone, email, or text messaging.

*b). Follow-up Questionnaire (Time 2):*

After one month, the patient will receive a follow-up survey via REDCap consisting of the study measures. Patients might also choose to set up an appointment with the PI to meet them at the health center to complete the questionnaire via iPad or hard-copy questionnaire.

Additionally, they may choose to complete this survey as a paper copy and return it to the PI in a return stamped envelope the PI will provide to the patient. The PI can also call the patient by telephone, read the questions aloud and record their answers within REDCap on the PI's iPad. Lastly, the PI will also consider meeting the patient at a public location if the patient prefers. These additional follow-up surveys will be kept in a locked file cabinet at the health center along with the other study documents which will only be accessible to the PI. If patients have not completed the follow-up survey within 10 days of the one-month follow-up date, two reminders will be sent by phone, email, or text messaging.

Once patient recruitment ceases, the survey will be closed. The de-identified data will be downloaded from REDCap and stored on a password protected computer. [name], the PI, and [name] (faculty advisor) will be the only persons with access to the data. The data will be cleaned and prepared for data analysis.

*Patient incentives:* At the completion of the baseline survey and app set up for intervention group patients and baseline survey and review of medication list for wait-list control patients, both groups will be given a \$25.00 gift card to compensate them for their time and effort in reviewing the medication list, using the app, entering key information and completing the surveys. Upon completion of the follow-up survey, both intervention group and wait-list control patients will receive an additional \$35.00 gift card for their time.

*Survey Study Measures:*

Patients will complete two surveys, representing medication and refill adherence and self-efficacy for appropriate medication use, medication knowledge and medication social support and the first will also gather demographic information. At the end of the study, the follow-up survey will gather information regarding the patient's feedback regarding the smartphone app or use of the printed out medication list. These surveys will take approximately five to ten minutes to complete.

**1. Medication and Refill Adherence:** Patients will complete the Adherence to Refills and Medications Scale (ARMS) to measure both medication and refill adherence. The ARMS is a global (continuous) 12-item scale, with a possible score of 12-48, patients with low ARMS scores indicate better adherence, it is valid and reliable in a low-literacy chronic disease population. Subscales include taking medications as prescribed (8 items) and refilling

medications on schedule (4 items). Responses range from 1 (none) to 4 (all of the time). Overall internal consistency has been established at Cronbach's alpha = 0.814.

**2. Self-efficacy for Appropriate Medication Use:** Patients will complete the Self-efficacy for Appropriate Medication Use Scale (SEAMS) to measure self-efficacy for medication adherence. It is a global (continuous) 13-item scale, with a possible score of 13-39. Patients with higher scores indicate higher levels of self-efficacy for medication adherence. It is valid and reliable in low-literacy chronic disease populations. Patients are asked their level of confidence about taking medications correctly. Responses range from 1 (not confident) to 3 (very confident). Overall internal consistency has been established at Cronbach's alpha = 0.89.

**3. Medication Knowledge:** Patients will complete the Okere-Renier Survey Medication Knowledge Subscale to measure medication knowledge. It is a global (continuous) 5-item scale with responses ranging from (1) strongly disagree to (5) strongly agree. A mean score is then calculated. Scores range from 5-25 with higher scores indicating greater medication knowledge. Overall internal consistency has been established at Cronbach's alpha = 0.83.

**4. Medication Social Support:** The measurement named Social Support: Medication-specific, consists of 8 items ranging from (0) never to (4) very often. It is a continuous measure, and a mean score is calculated. Higher scores reflect more medication support. Overall internal consistency has been established at Cronbach's alpha = 0.92.

**5. Intervention process** (intervention group only): Feedback about the smartphone app and additional features as well as an open-ended question will be a part of the second survey to ascertain opportunities and challenges of using the smartphone app and describe aspects of the app, they found most useful and least useful. Survey questions were developed and tested specifically for this purpose during the pilot study for use in this RCT. Patients will be asked if they plan to continue using the app after study completion.

**6. Hard copy medication list** (wait list control group only): Feedback about the usefulness of the hard copy medication list will be obtained at the end of the study.

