#### **D) RANDOMIZATION**

Once patients complete the baseline survey, patients will be randomized within each site to help reduce the likelihood of site bias. Patients will be randomized to either a wait list control group or the app intervention group. Randomization will be done by the PI automatically through REDCap. Intervention group patients will use the medication adherence app for 1-month and wait-list control group patients will receive a printed out copy of their medication list and have the name, dose, frequency and indication for their medications reviewed verbally with them by the PI. Both the intervention and wait-list control group will be contacted within the first week of enrolling in the study to see if they have any questions regarding the app or their medications in the case of the wait-list control. The follow-up measures will be completed by study patients in both the intervention and the wait-list control groups. At study completion, those randomized to the wait-list control group will be offered assistance by the PI to set up and use the app.

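### The PI, who knows the arm and taught the app, may read out and record the one-month self-report outcomes with no stated condition, and survey mode is not part of the analysis

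*Combined protocol and SAP*

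**What the plan says.** Section C, under Follow-up Questionnaire (Time 2), starts from a self-completed survey: "After one month, the patient will receive a follow-up survey via REDCap consisting of the study measures". It then lists other routes.

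- A visit: "Patients might also choose to set up an appointment with the PI to meet them at the health center", using the iPad or paper. The text does not say whether the PI helps with the answers.
- Paper by post: the patient may "complete this survey as a paper copy and return it to the PI in a return stamped envelope".
- Telephone: "The PI can also call the patient by telephone, read the questions aloud and record their answers within REDCap".
- A meeting elsewhere: "Lastly, the PI will also consider meeting the patient at a public location if the patient prefers". How the survey is completed there is not stated.

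The plan does not say when, or at whose request, the telephone route is used. At baseline, by contrast, the same section has patients answer on their own unless they ask for help, and the PI marks the answers only if the patient requests it.

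Section D states: "Randomization will be done by the PI automatically through REDCap". Under Sections D and E the PI also sets up and teaches the app in one arm and goes through the medication list verbally in the other. No blinding and no independent assessor are described. Adherence (ARMS), self-efficacy (SEAMS), medication knowledge and medication social support are all patient-reported. Section F compares change from baseline to one month by multiple linear regression and does not mention how the survey was completed.

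**The concern.** A patient asked about adherence over the telephone, by the person who taught them the app, may answer more favourably than on a form completed alone. In the intervention arm the same survey also asks for feedback on the app and whether the patient will go on using it, which may strengthen the effect.

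The baseline survey precedes randomisation, so help given there cannot depend on arm. The follow-up comes after it, and that is where the on-request limit is missing. Because the analysis uses change from baseline, a self-completed first survey followed by a PI-read second one puts any mode effect straight into the outcome.

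Nothing else in the plan would reveal this. The reliable change index deals with measurement error, not a systematic shift. Double data entry covers hard-copy surveys only. No field for survey mode is described, so neither the sponsor nor a reader could later tell how often the PI read the questions, or in which arm.

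**Working it through.** The documents give no sample size, SD, alpha or expected share of telephone surveys, so there is no figure of the plan's own to reproduce. What follows is an illustration. The shares, shifts, arm sizes and two-sided 5% level are all assumptions.

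**Formula for the bias.** Let fA and fC be the shares of the app and control arms whose follow-up survey is PI-read. Let bA and bC be the shift this causes toward a better score, in SDs of the analysed outcome. The bias in the arm comparison is

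B = fA × bA − fC × bC.

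**Formula for the false-positive rate.** With n per arm and no true effect, SE = √(2/n) in SD units. By the normal approximation, the probability of a significant result is

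Φ(B/SE − 1.96) + Φ(−B/SE − 1.96).

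**Worked case.** Take 30% PI-read in each arm, a 0.3 SD shift in the app arm, none in controls, and n = 50.

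- B = 0.3 × 0.3 − 0.3 × 0 = 0.09 SD.
- SE = √(2/50) = 0.20, so B/SE = 0.45.
- Probability = Φ(−1.51) + Φ(−2.41) = 0.066 + 0.008 = 0.074.

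**Results.**

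| Case | fA | fC | bA | bC | B (SD) | n = 30 | n = 50 | n = 100 |
|---|---|---|---|---|---|---|---|---|
| (a) Equal use, equal shift | 0.3 | 0.3 | 0.3 | 0.3 | 0 | 0.050 | 0.050 | 0.050 |
| (b) Little use, shift in app arm only | 0.1 | 0.1 | 0.3 | 0 | 0.03 | 0.052 | 0.053 | 0.055 |
| (c) Moderate use, shift in app arm only | 0.3 | 0.3 | 0.3 | 0 | 0.09 | 0.064 | 0.074 | 0.098 |
| (d) Unequal use, equal shift | 0.5 | 0.2 | 0.3 | 0.3 | 0.09 | 0.064 | 0.074 | 0.098 |
| (e) Heavy use, large shift in app arm only | 0.5 | 0.5 | 0.5 | 0 | 0.25 | 0.162 | 0.240 | 0.424 |

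**Reading the table.** Bias needs a difference between arms, either in the shift (b, c, e) or in the use of the mode (d). Where both are equal (a), it cancels. Exchanging the arms reverses the sign, so the algebra does not fix the direction. With no PI-read surveys in either arm, B = 0 for this component. Over-reporting by patients who know their arm would remain, and the documents give nothing from which to size it.

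**The case against.** The case against has four parts.

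**Self-completion is already the default.** A reader might infer from the list of routes that PI-read and self-completed surveys stand on equal terms. The text does not support that: the REDCap survey goes to every patient, and the others are worded as additions. This stands. What remains is that the telephone route has no condition and that mode is not in the analysis.

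**The PI deals with both arms.** A reader might infer a definite bias in favour of the app. The documents do not establish it. Controls also have their medications reviewed by the PI, both arms are contacted in the first week and receive the same follow-up payment, and controls too give feedback on what they received. They may equally want to please the PI. This stands, and it makes the bias possible rather than certain. The two relationships still differ, and unequal use of the mode would be enough on its own.

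**Self-completion is not a cure.** A reader might infer that the self-completed modes avoid social desirability altogether. They do not: patients know their arm, and paper forms go back to the PI, who has access to the data. Only the interviewer component is reduced.

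**Restriction has a price.** Eligibility asks for speaking and understanding English, not for reading it, so removing the read-aloud option could trade measurement bias for missing data. Reminders begin only when the survey is 10 days overdue, so waiting for both to fail would make those measurements late. Patients who end up PI-read would also differ from the rest, so leaving them out does not isolate the interviewer's effect. All of this stands. It argues for conditions on the mode rather than a ban, and for treating the sensitivity analysis as supportive only.

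**Conclusion.** The point holds as a gap in the follow-up procedure and in Section F. A PI who knows the allocation and taught the app may collect self-reported outcomes by interview, with no stated condition and no provision for mode in the analysis. If the use or the effect of that mode differs between arms, the comparison of change scores is biased.

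The size is unknown. In the cases shown it runs from zero to 0.25 SD, with a false-positive rate per outcome of 5% to 24% at 50 per arm. The upper end assumes half of each arm is PI-read, a 0.5 SD shift in the app arm and none in controls. The moderate case of 0.09 SD gives about 7% at 50 per arm and 10% at 100. None of these inputs comes from the documents, so the figures show only what could happen. The case for acting is that the change is cheap and that, without a record of mode, the effect can be neither bounded nor ruled out.

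**What to change.** **Section C, follow-up questionnaire.** Keep the REDCap link, or mailed paper, as the standard mode in both arms. Allow PI-read follow-up only when the patient asks for help, cannot self-complete, or has not responded by a fixed point defined identically for both arms. Use a fixed script. In choosing that point, note that waiting until both reminders have failed puts the survey more than 10 days past the one-month date.

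**REDCap.** Record the mode at both surveys (self-completed alone, self-completed with the PI present, PI-read) and the date the follow-up was completed. Baseline mode is needed because the outcome is a change score. The fields should be in place before follow-up collection starts.

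**Section F.** Tabulate mode by arm. Add a supportive sensitivity analysis that repeats the main regressions without PI-read follow-up surveys. State whether surveys completed with the PI present are kept, and that mode is a post-randomisation choice, so agreement or disagreement with the main result does not by itself measure interviewer bias.

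**Cost.** One or two REDCap fields, a short rule on mode, one table and one extra analysis. A few patients will have a slightly later follow-up. No extra staff are needed.

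### Does closing an unnamed survey when recruitment ends, with no last day stated for Time 2, put the one-month follow-up data at risk?

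*Combined protocol and SAP*

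**What the plan says.** Section C, under Follow-up Questionnaire (Time 2), states: "Once patient recruitment ceases, the survey will be closed". Shortly afterwards it says: "The de-identified data will be downloaded from REDCap and stored on a password protected computer". Cleaning and preparation for analysis follow. Neither closing nor download has a calendar date.

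The same section describes two surveys, one at baseline (Time 1) and one at follow-up (Time 2). On the timing of the second it says: "After one month, the patient will receive a follow-up survey via REDCap consisting of the study measures". It then provides: "If patients have not completed the follow-up survey within 10 days of the one-month follow-up date, two reminders will be sent". Follow-up may also be completed on paper by post, by telephone, or in person.

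Section D (Randomization) has both groups complete the follow-up measures. Section F (Data Analysis) analyses change from baseline to one month and classifies each patient's change against a reliable change index.

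**The concern.** The closing sentence stands under the Time 2 heading, directly after the follow-up reminder rule and before the download. A reader could take it to mean that the follow-up survey closes on the day recruitment stops. The last patients enrolled would then lose the online route before their follow-up was due.

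If the sentence means the baseline survey instead, Time 2 has an opening time and a reminder trigger but no end. It is then unwritten which late responses count as one-month values in the change scores and the reliable change classification, and when the data set is taken for analysis. The PI runs randomisation, delivers both arms, may administer follow-up and has access to the data. A rule left unwritten in that setting invites a question about discretion.

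**Working it through.** The plan gives no figure to reproduce. The check compares the text on each reading and adds up a few days.

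**1. Which survey closes: usage.** Apart from the closing sentence, the bare phrase *the survey* occurs four times, and each time it means baseline:
- Section B, patients available in person: "either give them a hard copy of the survey"
- Section B, same paragraph: "While patients complete the survey, the PI will remain in the room to be available should questions arise"
- Section C, Baseline Data Collection: "indicate their responses on the survey"
- Section C, REDCap surveys: "patients might access the survey and complete consent and the study measures by using the REDCap survey link"

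Time 2 is called the follow-up survey five times in section C (including Survey Study Measures) and the second survey once (Intervention process): 5 + 1 = 6 labelled uses. The pattern is not perfect. Section C also refers to Time 2 without a label, as this survey and as the questionnaire, although the preceding text makes the meaning clear there. Usage therefore leans towards baseline but does not settle the matter.

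**2. Which survey closes: timing.** Inputs: follow-up is due one month after baseline (assumed 28 to 31 days), and reminders start if there is no response within 10 days of that date.
- Follow-up due for a patient enrolled on the last recruitment day: day 28 to 31.
- Reminders from: 28 + 10 = 38 to 31 + 10 = 41 days.

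If the follow-up survey closed at the end of recruitment, online follow-up would end before it was due for anyone enrolled in the last 28 to 31 days, and before reminders for anyone enrolled in the last 38 to 41 days. This conflicts with the follow-up and reminder rules in section C and with section D. If the baseline survey closes, nothing conflicts and the loss of Time 2 data is zero. A looser reading, in which the author means the end of data collection as a whole, also costs nothing.

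**3. Last day for Time 2.** The documents fix the start and the reminder trigger and limit contact to two reminders. The 10 days is a trigger and not a cut-off, and the interval between reminders is not stated. The documents do not say that a very late response counts, nor that it does not. The procedure is the same in both groups.

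**4. Download.** The order is given: recruitment ends, the survey closes, data are downloaded, data are cleaned. Section C adds that the double-entry check of paper forms is finished before analysis starts. Section F needs Time 2 values to compute change, so the analysis data set cannot be complete until follow-up is. No interim analysis is described, so no result is shown to depend on a download date.

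**The case for a change.** The strongest case for a change is that neither reading supplies a complete rule. If the baseline survey closes, Time 2 has no end; if the follow-up survey closes, the plan contradicts itself. Late responses are foreseeable, since the plan provides reminders and several routes of return. A response well after one month may reflect a different period of app use yet enter as a one-month value. A window written in advance would cost only a few sentences and would remove discretion from an investigator who is involved at every stage.

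Part of this stands. No last day and no download date are given, and fixing a window before looking at the outcomes is good practice.

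The consequences are not shown. The silence on late responses does not amount to a rule admitting them. No text says that the PI alone would decide: a faculty advisor also has access to the data, and randomisation, though done by the PI, runs automatically through REDCap. No mechanism is shown by which late responses would favour one group. Nor do the documents supply a basis for a particular last day; any figure would rest on an assumed reminder interval.

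**Conclusion.** No change is called for. The closing sentence is loosely worded, but the protocol's own follow-up rules leave the consent and baseline survey as the only literal reading without contradiction, and on that reading no Time 2 data are lost. The missing last day and download date are details that an analyst would settle before analysis, by waiting for the last randomised patient's follow-up and deciding how to treat late responses.

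The shown effect on results is nil. How many responses might be late cannot be worked out, because the documents give no sample size, accrual rate or expected response times. The conclusion assumes that every randomised patient is followed to Time 2, as sections C and D require, and that late responses are handled alike in both groups.

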## F. DATA ANALYSIS

IBM SPSS Statistics will be used for the quantitative summarization of the effects of the use of the app on the change in self-efficacy (SEAMS) and medication adherence (ARMS) from baseline to 1-month. Descriptive statistics will summarize sample characteristics and study measures. Raw change values from T1 to T2 in the adherence (ARMS), self-efficacy (SEAMS), medication social support, and medication knowledge scores will be calculated. Tests on the effects of the Medisafe app on those outcome measures will be conducted using multiple linear regression models. Given measurement error inherent in self-report measures, a reliable change index (RCI) criterium will be generated for each self-report measure. Each patient's raw change value will be evaluated against that criterium to determine whether the change was reliable or not and the direction of that change.

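### Does it matter that the medication knowledge score is called a mean but given the range of a sum?

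*Combined protocol and SAP*

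**What the plan says.** In section C, under Survey Study Measures, item 3 (Medication Knowledge), the instrument is a "5-item scale with responses ranging from (1) strongly disagree to (5) strongly agree". The scoring follows directly: "A mean score is then calculated. Scores range from 5-25 with higher scores indicating greater medication knowledge". The same item gives a Cronbach's alpha of 0.83.

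The neighbouring measures follow different conventions. ARMS (12 items scored 1-4, range 12-48) and SEAMS (13 items scored 1-3, range 13-39) have the ranges of sums. Medication Social Support, the next item, is scored as a mean with no range stated: "It is a continuous measure, and a mean score is calculated".

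Section F (Data Analysis) uses the knowledge score in three ways. First, "Raw change values from T1 to T2 in the adherence (ARMS), self-efficacy (SEAMS), medication social support, and medication knowledge scores will be calculated". Second, the app's effect on these outcomes is tested by multiple linear regression. Third, "a reliable change index (RCI) criterium will be generated for each self-report measure", and each patient's raw change is compared with that criterion. Section F does not say which scale the knowledge score is on.

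**The concern.** Two adjacent sentences contradict each other. A knowledge score of 4.0, perfectly ordinary for a mean, would lie below the minimum of 5 that the protocol gives. The other scales do not settle the matter, since two are sums and one is a mean.

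Every unstandardised quantity for this outcome is therefore undefined up to a factor of 5. The largest possible change is 4 points on one reading and 20 on the other, so a 1-point effect is 25% of the possible change or 5% of it.

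Two routes could carry the ambiguity into results. If the standard deviation behind the reliable change criterion came from one scale and the patients' changes from the other, the criterion would be wrong by a factor of 5. And if items are missing, a sum of the answered items is no longer five times their mean. Skipped items are possible because, at follow-up, "they may choose to complete this survey as a paper copy and return it to the PI in a return stamped envelope".

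**Working it through.** **Inputs from the protocol.** Items k = 5; item scores 1 to 5; stated range 5-25; alpha = 0.83. The protocol gives no standard deviation, formula or confidence level for the reliable change index, so those used below are assumptions.

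**Step 1: the stated range.** A mean of k items scored lo to hi lies in [lo, hi]; a sum lies in [k x lo, k x hi].

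| Measure | Sum | Mean | Stated |
|---|---|---|---|
| ARMS (12 items, 1-4) | 12-48 | 1-4 | 12-48 |
| SEAMS (13 items, 1-3) | 13-39 | 1-3 | 13-39 |
| Medication knowledge (5 items, 1-5) | 5-25 | 1-5 | 5-25, called a mean |
| Social support (8 items, 0-4) | 0-32 | 0-4 | none, called a mean |

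The range 5-25 is reproduced by the sum and not by the mean. The contradiction is confirmed.

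**Step 2: effect on the analysis, complete items.** Let M be the mean and S = 5M the sum.

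- Change: S2 - S1 = 5(M2 - M1).
- Regression: multiplying the outcome by 5 (and its baseline too, if that is a covariate) multiplies the treatment coefficient and its standard error by 5. Their ratio t, and hence the p-value, is unchanged.
- Reliable change: assume the Jacobson-Truax form with alpha as the reliability. The criterion is z x SD x sqrt(2(1 - 0.83)) = z x SD x 0.583, which is 1.143 SD at 95% and 0.959 SD at 90%. Because SD(S) = 5 SD(M), the criterion also scales by 5, and each patient falls on the same side of it.

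For example, assume SD = 3 on the sum, hence 0.6 on the mean. At 95% the criterion is 1.143 x 3 = 3.43 of a possible 20, or 1.143 x 0.6 = 0.69 of a possible 4. Both are 17.1% of the maximum change.

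A simulated data set (100 patients, 50 per group, complete items, baseline-adjusted regression) illustrates the identity:

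| | Mean | Sum |
|---|---|---|
| Coefficient | 0.097 | 0.486 |
| Standard error | 0.101 | 0.507 |
| t | 0.959 | 0.959 |
| p | 0.340 | 0.340 |
| Reliable change criterion (95%) | 0.890 | 4.449 |

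Every patient's reliable-change class was identical.

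**Step 3: mixed scales.** Assume a sum-scale SD of 2 is applied to mean-scale changes. The 95% criterion becomes 1.143 x 2 = 2.29 instead of 1.143 x 0.4 = 0.46. In the same simulated data, mixing classed 0% as reliably changed, against 13% with matched scales. The error would be large if made.

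**Step 4: missing items.** Four items answered 4 and one blank give a mean of 4.0, equivalent to a sum of 20. Adding only the answered items gives 16, a gap of 4 points. If an incomplete sum is instead set to missing, no such gap arises. The protocol prescribes neither.

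**The case for a change.** The best case for a correction is that the inconsistency is certain, concerns an analysed outcome and takes one line to repair. Section F gives no formula or source of standard deviation for the reliable change criterion, so nothing written down guards against mixing scales. Double entry of paper forms checks transcription, not scoring.

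The inconsistency stands; the consequences attached to it mostly do not. Section F generates one criterion per measure and compares each patient's raw change with it, which on a natural reading means one score per measure throughout. Mixing scales would be an analyst's mistake, not a result of following the plan. The missing formula, standard deviation source and missing-item rule are omissions that affect all four scales alike, and settling whether knowledge is a mean or a sum would supply none of them.

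Nor is the ambiguity likely to reach a reader of the results. The ranges 1-5 and 5-25 share only the value 5, and Section F plans descriptive statistics for the study measures, so a reported group average of, say, 4 or 20 shows which scale was used. The units of the change, coefficient and criterion then follow.

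**Conclusion.** The protocol mislabels the medication knowledge score: it describes a mean and prints the range of a sum. This is a clerical slip. The two readings differ by a constant factor of exactly 5, and no test, direction, standardised effect or reliable-change class depends on which is used, provided the items are complete and one scale is used throughout.

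The outcome is also not the leading one. Section F opens with change in self-efficacy and adherence, whose stated ranges reproduce correctly, and no sample size or decision threshold in the document is expressed in knowledge-score units. An analyst will score the instrument by its own instructions, keep one scale for the change, the model and the criterion, and name it in the report. The mixed-scale and missing-item figures rest on assumed standard deviations, an assumed index formula and an assumed scoring of incomplete forms; they show what a separate error could do, not what this plan does. No change to the plan is needed.
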